7.2 Primary Analysis

The primary analysis will occur when all subjects treated with at least 1 dose of talimogene laherparepvec or pembrolizumab have had the opportunity to be followed for at least 24 weeks for tumor assessment. The database will be cleaned and a locked database will be used for this analysis.

Before the primary analysis, ad hoc analyses may be conducted to support program level activities.

7.3 Final Analysis

The final analysis will occur when all subjects have completed the study. The database will be cleaned and a locked database will be used for this analysis.

8. Data Screening and Acceptance

8.1 General Principles

The objective of the data screening is to assess the quantity, quality, and statistical characteristics of the data relative to the requirements of the planned analyses.

8.2 Data Handling and Electronic Transfer of Data

The Amgen Global Study Operations-Data Management (GSO-DM) department will provide all data to be used in the planned analyses. This study will use the RAVE database.

8.3 Handling of Missing and Incomplete Data

Every effort will be made to obtain complete data in the clinical study. Partial or missing dates of adverse events and concomitant medications will be imputed. Adverse events with missing IP relatedness, seriousness, or CTCAE severity grades are included in TEAE as long as the events qualify for the reporting period. Events with missing relatedness, seriousness, and severity grades will be excluded from treatment-related, serious, and with a CTCAE grade of 3 or higher AE analysis, respectively. [REDACTED]

[REDACTED]

[REDACTED]

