Examples of such events include invasive or malignant cancers, intensive treatment in an emergency room or at home for allergic bronchospasm, blood dyscrasias or convulsions that do not result in hospitalization, or development of drug dependency or drug abuse.

Recording Adverse Events and Serious Adverse Events

Adverse Event and Serious Adverse Event Recording

- When an adverse event or serious adverse event occurs, it is the responsibility of the investigator to review all documentation (eg, hospital progress notes, laboratory, and diagnostics reports) related to the event.
- The investigator will then record all relevant adverse event/serious adverse event information in the Event case report form (CRF). Additionally, the investigator is required to report a fatal adverse event on the Event CRF.
- The investigator must assign the following adverse event attributes:
 - Adverse event diagnosis or syndrome(s), if known (if not known, signs or symptoms);
 - Dates of onset and resolution (if resolved);
 - **Did the event start prior to first dose of investigational product, other protocol-required therapies;**
 - **Assessment of seriousness;**
 - Severity (or toxicity defined below);
 - Assessment of relatedness to talimogene laherparepvec, pembrolizumab and/or study conduct;
 - Action taken; **and**
 - **Outcome of event**
- If the severity of an adverse event worsens from the date of onset to the date of resolution, record a single event for each increased level of severity on the Events CRF.
- It is not acceptable for the investigator to send photocopies of the subject's medical records to sponsor in lieu of completion of the Events CRF page.

Adverse Event and Serious Adverse Event Recording

- If specifically requested, the investigator may need to provide additional follow-up information, such as discharge summaries, medical records, or extracts from the medical records. In this case, all subject identifiers, with the exception of the subject number, will be blinded on the copies of the medical records before submission to Amgen.
- The investigator will attempt to establish a diagnosis of the event based on signs, symptoms, and/or other clinical information. In such cases, the diagnosis (not the individual signs/symptoms) will be documented as the adverse event/serious adverse event.

Evaluating Adverse Events and Serious Adverse Events

Assessment of Severity

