The investigator will make an assessment of severity for each adverse event and serious adverse event reported during the study. The assessment of severity will be based on the Common Terminology Criteria for Adverse Events, version 5.0 which is available at the following location:

http://ctep.cancer.gov/protocolDevelopment/electronic_applications/ctc.htm.

Assessment of Causality

- The investigator is obligated to assess the relationship between talimogene laherparepvec, pembrolizumab and/or study-mandated procedure and each occurrence of each adverse event/serious adverse event.
- Relatedness means that there are facts or reasons to support a relationship between investigational product and the event.
- The investigator will use clinical judgment to determine the relationship.
- Alternative causes, such as underlying disease(s), concomitant therapy, and other risk factors, as well as the temporal relationship of the event to study treatment administration will be considered and investigated.
- The investigator will also consult the Investigator's Brochure and/or Product Information, for marketed products, in his/her assessment.
- For each adverse event/serious adverse event, the investigator must document in the medical notes that he/she has reviewed the adverse event/serious adverse event and has provided an assessment of causality.
- There may be situations in which a serious adverse event has occurred and the investigator has minimal information to include in the initial report. However, it is very important that the investigator always make an assessment of causality for every event before the initial transmission of the serious adverse event data.

Assessment of Causality

- The investigator may change his/her opinion of causality in light of follow-up information and send a serious adverse event follow-up report with the updated causality assessment.
- The causality assessment is 1 of the criteria used when determining regulatory reporting requirements.

Follow-up of Adverse Event and Serious Adverse Event

- The investigator is obligated to perform or arrange for the conduct of supplemental measurements and/or evaluations as medically indicated or as requested by Amgen to elucidate the nature and/or causality of the adverse event or serious adverse event as fully as possible. This may include additional laboratory tests or investigations, histopathological examinations, or consultation with other health care professionals.

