2.1 Objectives and Endpoints

Objectives	Endpoints
Primary	

 • To evaluate the efficacy of talimogene laherparepvec in combination with pembrolizumab as assessed by objective response rate (ORR) in subjects with unresectable/metastatic stage IIIB-IVM1d melanoma who have progressed on prior anti-PD-1 therapy 	
 • Overall response (complete response [CR]+partial response [PR]) (by investigator assessment using modified RECIST v1.1)
Key Secondary	

 • To evaluate the efficacy of talimogene laherparepvec in combination with pembrolizumab, as assessed by: 
 ○ Complete response rate (CRR), best overall response (BOR), durable response rate (DRR), duration of response (DOR), and disease control rate (DCR) ○ ORR using modified irRC-RECIST ○ Progression free survival (PFS) ○ Overall survival (OS) 	
 • Complete response, BOR, durable response, DOR and disease control, (investigator assessment using modified RECIST 1.1 and modified irRC-RECIST) and overall response using modified irRC-RECIST by investigator assessment • PFS (by investigator assessment using modified RECIST 1.1 and modified irRC-RECIST) • OS

 • To evaluate the safety of talimogene laherparepvec in combination with pembrolizumab as assessed by incidence of treatment-emergent and treatment-related adverse events, and abnormal laboratory tests in patients who have progressed on prior anti-PD-1 therapy 	
 • Incidence of treatment-emergent and treatment-related adverse events (all adverse events, grade ≥ 3 adverse events, serious adverse events, fatal adverse events, adverse events defined as events of interest), and abnormal laboratory tests

• To evaluate time to subsequent anticancer therapy	
• Time to subsequent anticancer therapy
---	---

Exploratory	
	

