9.5.3 Analyses of Exploratory Efficacy Endpoint(s)

9.6 Safety Analyses

9.6.1 Adverse Events

Safety analyses will be conducted separately for each cohort on Safety Analysis Set (SAS). The Medical Dictionary for Regulatory Activities (MedDRA) version 21.1 or later will be used to code all adverse events (AE). The CTCAE version 5.0 or later will be used to grade severity of adverse events.

The subject incidence of AEs will be summarized for all treatment-emergent AEs, serious AEs, AEs leading to withdrawal of investigational product, grade 3 or 4 AEs, fatal AEs, events of interests (EOIs) for talimogene laherparepvec and pembrolizumab events of clinical interest (ECI). Subject incidence of EOI/ECIs will be summarized by the EOI/ECI categories. Preferred terms within each EOI/ECI category will also be summarized.

The subject incidence of all treatment-related AEs, serious AEs, AEs leading to withdrawal of investigational product, grade ≥ 3 AEs, fatal AEs, and EOs for talimogene laherparepvec will be tabulated by system organ class and preferred term in descending order of frequency.

Summaries of treatment-emergent and serious AEs occurring in at least 5% of the subjects by preferred term will be provided in descending order of frequency.

A Listing will be provided for treatment-emergent adverse events and treatment-emergent serious adverse events. In addition, death on study will be listed.

Potential or known unintended exposure to talimogene laherparepvec, related suspected signs or symptoms, and detection of talimogene laherparepvec in a subject's household member, caregiver, or healthcare provider will be summarized.

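### SAP 8.3 handles missing relatedness, seriousness or grade as not qualifying, so the rule can understate but never overstate the treatment-related, serious and grade 3 or higher incidences

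*SAP*

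**What the plan says.** SAP 8.3 has two linked rules for adverse events with an incomplete record.

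- **Overall table.** Events lacking relatedness, seriousness or grade "are included in TEAE as long as the events qualify for the reporting period".
- **Tables defined by those fields.** The next sentence reads: "Events with missing relatedness, seriousness, and severity grades will be excluded from treatment-related, serious, and with a CTCAE grade of 3 or higher". It closes by applying this respectively, and that matters: missing relatedness removes an event from the treatment-related analysis, missing seriousness from the serious analysis, and missing grade from the grade 3 or higher analysis.

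The affected summaries are named in SAP 9.6.1: "The subject incidence of all treatment-related AEs, serious AEs, AEs leading to withdrawal of investigational product, grade ≥ 3 AEs, fatal AEs". The unit is the subject with at least one qualifying event, and safety is analysed by cohort. SAP 2.1 lists these incidences among the key secondary endpoints: "Incidence of treatment-emergent and treatment-related adverse events (all adverse events, grade ≥ 3 adverse events, serious adverse events, fatal adverse events".

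On collection, Protocol Section 12.4 (Appendix 4) is firm: "The investigator must assign the following adverse event attributes", and the list that follows includes seriousness, severity and relatedness. For serious events it adds that "it is very important that the investigator always make an assessment of causality for every event before the initial transmission" of the data.

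**The concern.** Leaving an event out of a table because the defining field is blank has the same effect as filling the blank with the benign answer. The possible error runs one way, towards a more favourable safety profile.

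Three features of this trial give that some weight. First, it is single-arm, so an understated absolute incidence is not offset by a comparator handled in the same way. Second, the safety tables are produced for cohorts of 27, 15, 15 and 15, where one subject moves the percentage visibly. Third, the rule goes against the SAP's own habit. SAP Section 5 counts a subject with no post-baseline tumor assessment as a non-responder, and by default treats an event on the first dosing day as treatment-emergent. Both settle doubt against the treatment, whereas this rule settles it in favour.

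In the visible text nothing would show a reader of the incidence tables whether the rule had changed them.

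**Working it through.** **Inputs**

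- Enrolled: 72 in total, 27 in cohort 1 and 15 in each of cohorts 2, 3 and 4 (SAP 3.2).
- Denominator: the Safety Analysis Set, which requires at least one dose of either product (SAP 6.2). I assume that all 72 were dosed; if fewer were, one subject weighs slightly more.
- Unit: subject incidence (SAP 9.6.1).
- Share of events with a missing field, and true incidence: not in the documents. Assumed below and shown as a range.

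The plan states no figure for missingness or its effect, so there is none to reproduce.

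**Step 1: direction.** A subject counts in, say, the grade 3 or higher table if at least one event is recorded at grade 3 or higher. Removing events with a blank grade can only remove subjects from the numerator, and the denominator does not change. So, taking recorded values as correct, reported incidence ≤ true incidence. Equality holds when the blank belongs to an event that truly does not qualify, or when the subject is already counted through another event.

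**Step 2: weight of one lost subject (1/n).**

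- Pooled: 1/72 = 1.4 points
- Cohort 1: 1/27 = 3.7 points
- Cohort 2, 3 or 4: 1/15 = 6.7 points

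**Step 3: expected loss under assumptions.** Let p be the true subject incidence, q the chance that a grade is missing (independent between events), and m the number of truly grade 3 or higher events per affected subject. The subject is lost only if all m grades are missing, so:

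reported = p × (1 − q^m), and loss = p × q^m

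With p assumed at 20/72 = 27.8%, the loss in percentage points is:

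| q | m = 1 | m = 2 | m = 3 |
|---|---|---|---|
| 1% | 0.28 | 0.003 | < 0.001 |
| 5% | 1.39 | 0.07 | 0.003 |
| 10% | 2.78 | 0.28 | 0.03 |

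The loss is close to proportional to missingness when affected subjects have a single qualifying event, and almost vanishes when they have two or more.

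**Step 4: against sampling error.** Clopper-Pearson 95% limits for the assumed pooled case:

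- 20/72 = 27.8% (17.9 to 39.6)
- 19/72 = 26.4% (16.7 to 38.1), one subject lost
- 18/72 = 25.0% (15.5 to 36.6), two subjects lost

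A shift of one or two subjects is small beside an interval about 22 points wide (39.6 − 17.9 = 21.7). It is a systematic shift, however, and the interval does not reflect it.

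**Step 5: the reverse rule.** Counting missing as qualifying raises the incidence by at most 1/n for each subject with no other qualifying event, and by 0 for a subject already counted. It has the same unit weight in the opposite direction.

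**The case against.** The strongest reply is that the rule covers a residue that may be close to empty. The protocol makes all three attributes mandatory, asks for causality before a serious event is first transmitted, and provides for ongoing source data verification (Section 12.3). The SAP has the database cleaned and locked before the primary and final analyses (7.2, 7.3). Treatment-emergent events and treatment-emergent serious events are listed, as are deaths on study (9.6.1). All analyses are descriptive, and the rule is explicit and reproducible. This stands as an argument about size. It does not change the direction, and Section 12.4 itself foresees serious events first reported with minimal information.

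A second reply is that worst-case counting replaces one one-sided error with another: a grade 1 event with a blank grade would enter the grade 3 or higher row. That is fair for grade, which is why the fix puts it in a sensitivity row. For relatedness and seriousness the possible overstatement is a real but bounded cost.

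A third reply is that redacted text follows the rule directly and may bear on it. So the absence of a count or sensitivity analysis can be asserted only for the text that can be read.

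A reader might go further and infer that every missing field lowers the reported toxicity. The documents do not support that. Overall treatment-emergent incidence is untouched, a missing field acts only on the analyses it defines, and Step 1 shows when nothing is lost. A reader might also infer that blanks cluster in subjects who deteriorate or leave early. Nothing in the documents says so.

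**Conclusion.** The point holds as a one-sided rule of unknown but possibly small effect. The exclusion can understate, and never overstate, the treatment-related, serious and grade 3 or higher subject incidences, which are key secondary endpoints. The cost is 1.4 points pooled, 3.7 points in cohort 1 or 6.7 points in a 15-subject cohort for each subject whose only qualifying event has the field missing. This rests on all enrolled subjects having been treated. How many such subjects there would be cannot be derived from the documents, so no overall bias figure can be given; the Step 3 table is illustration only. The gap that can be stated plainly is that the visible SAP neither counts these events nor tests the rule. It is a cheap improvement and does not undermine the safety analysis.

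**What to change.** Replace the exclusion sentence in SAP 8.3 with a rule along these lines:

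- **Relatedness missing:** the event counts as related to study therapy.
- **Seriousness missing:** the event counts as serious.
- **Grade missing:** the event appears in its own row, by cohort. A sensitivity row adds it to grade 3 or higher; the main grade 3 or higher row stays restricted to recorded grades.
- **Every affected table:** a footnote gives the number of events classified under the rule.

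Keep the existing sentence that retains these events in the overall treatment-emergent table. If the redacted text already covers any of this, align the two.

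The cost is a sentence or two in the SAP, a programming flag and a footnote, with no new data. The downside is that the incidences may be slightly less favourable, and could be overstated if the events did not truly qualify. The footnoted counts let a reader judge how far that goes, and if nothing is missing the tables do not change.

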8.4 Detection of Bias

Lack of protocol compliance may introduce potential bias in the estimation of protocol endpoints. All important protocol deviations (IPDs) will be reported, documented and stored in eClinical (a clinical trial management system). IPD reports will be produced [REDACTED] by the study manager and will be regularly reviewed in the study team's IPD review meetings as well as before analysis.

8.5 Outliers

Descriptive statistics will be used to identify potential outliers in key variables. Suspected outliers will be included in all analyses unless there is sufficient scientific justification to exclude them.

8.6 Distributional Characteristics

All binary endpoints will follow a binomial distribution. The KM estimates for the probability of time-to endpoints are based on non-parametric methods

8.7 Validation of Statistical Analyses

Programs will be developed and maintained, and output will be verified in accordance with current risk-based quality control procedures.

Tables, figures, and listings will be produced with validated standard macro programs where standard macros can produce the specified outputs.

The production environment for statistical analyses consists of Amgen-supported versions of statistical analysis software; for example, the SAS System version 9.4 or later and qualified R.

9. Statistical Methods of Analysis

9.1 General Considerations

Unless otherwise specified, all safety analysis will be performed on the SAS and all efficacy analysis on the FAS. All analyses will be descriptive with no formal hypothesis testing. Analyses will be performed separately for each cohort. In addition, analyses with cohorts pooled together (all cohorts pooled, cohorts 1 and 2 pooled, and cohorts 3 and 4 pooled) will be performed. Cohorts stopped for futility will not be pooled with other cohorts. Cohort data collected on the CRF will be used in the analysis. Cohort data will be checked and reviewed during the study to ensure that subjects are recorded in the correct cohort for analyses prior to database lock.

Continuous variables will be summarized by the non-missing sample size (n), mean, standard deviation, median, first and third quartiles, minimum, and maximum.

Categorical variables will be summarized by the n and percentage in each category.

Proportions and the corresponding 95% exact CIs will be provided ([Clopper and Pearson, 1934](#)).

[REDACTED], time to event endpoints will be summarized with Kaplan-Meier (KM) ([Kaplan and Meier, 1958](#)) curves, KM estimates at selected time points, KM quartiles (when estimable), the number of subjects with events and the number of subjects censored. Accompanying 2-sided 95% CI for KM quartiles ([Brookmeyer and Crowley, 1982](#)) and KM estimates will be provided.

